This study is a single-center, parallel-group, randomized controlled trial with an intervention group and an active control group. The trial will be conducted at Van Regional Training and Research Hospital, Endocrinology and Metabolism Diseases Outpatient Clinic (Van, Türkiye). A total of 72 participants diagnosed with T2DM, aged between 18 and 45 years, who meet the eligibility criteria and provide informed consent, will be included. The planned study duration is 24 months, including preparation, recruitment, intervention, follow-up, data analysis, and reporting. The intervention period for each participant is 12 weeks.

Participants

Inclusion criteria include: (1) diagnosis of type 2 diabetes mellitus, (2) age 18–45 years, (3) ability to communicate in Turkish, (4) literacy, (5) access to the internet and ability to use a smartphone, tablet, or computer, (6) no severe physical or mental health condition that would prevent participation, and (7) willingness to provide informed consent and participate in digital follow-up.

Exclusion criteria include: (1) presence of advanced diabetic retinopathy with severe visual impairment that prevents use of digital tools, (2) diagnosis of type 1 diabetes or gestational diabetes, (3) refusal to share necessary information for the study, and (4) participation in another structured DSMES program that could interfere with the intervention.

Withdrawal criteria include: (1) participant request to withdraw at any time, (2) inability to complete follow-up assessments, (3) interruption of internet access or digital communication for more than two weeks, (4) failure to start the program within four weeks after enrollment or participation in less than 50% of the planned intervention, (5) initiation of GLP-1 receptor agonist therapy during the study period, and (6) any new health condition deemed by the investigator to make continued participation inappropriate.

Randomization and Blinding

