After baseline assessment, participants will be randomized in a 1:1 ratio to the intervention or active control group using stratified block randomization. Stratification will be based on baseline HbA1c levels (6.5–9% and > 9%) to ensure balanced glycemic status across groups. The randomization list will be generated by an independent researcher. Participants will not be explicitly informed of their group allocation (single-blind design); however, due to the nature of the intervention, the research team delivering the DSMES program cannot be blinded.

Intervention Group: Nurse-Led Digital DSMES Program

Participants in the intervention group will receive a 12-week nurse-led digital DSMES program delivered through a dedicated digital platform. The program is structured according to the ADCES7™ self-care behavior framework (healthy coping, healthy eating, being active, monitoring, taking medication, problem solving, and reducing risks). Key components of the program include:

1. Structured Digital Education Modules: Educational content on T2DM pathophysiology, treatment, self-monitoring, nutrition, physical activity, medication adherence, complication prevention, and psychosocial coping strategies, presented in user-friendly language with visual aids.
2. Interactive Self-Monitoring Tools: Digital forms and tracking cards that allow participants to record glycemic values (fasting and postprandial glucose), HbA1c (when available), blood pressure (if applicable), and self-care behaviors related to the ADCES7™ domains. Participants will receive automated reminders to encourage regular data entry.
3. Nurse-Led Individualized Counseling and Support: Regularly scheduled synchronous and asynchronous communications (such as messaging or calls) with a nurse trained in diabetes education. The nurse will review participants' data, provide tailored feedback, reinforce educational messages, support goal-setting and problem solving, and offer motivational encouragement.
4. Digital Support and Chatbot: A chatbot or FAQ component to provide quick answers to common questions about diabetes management, medication use, hypoglycemia management, and lifestyle behaviors, supplementing nurse support.

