5. Multidisciplinary Collaboration (as needed): When necessary, participants may be guided to consult their physician, dietitian, or psychologist for issues identified during the digital follow-up. The nurse will facilitate communication and encourage participants to seek appropriate in-person or telehealth services.

Participants in the intervention group will be encouraged to engage with the platform regularly, follow the educational modules according to the suggested schedule, record their data, and communicate with the nurse as needed.

Active Control Group: Standard Digital Education

Participants in the active control group will be provided with access to the standard Type 2 Diabetes Education Brochure prepared by the Turkish Ministry of Health in PDF format via the digital platform. They will also be able to enter their basic glycemic data into the system. However, they will not receive individualized nurse-led digital counseling, structured DSMES modules based on ADCES7™, or chatbot-based interactive support. This design allows comparison of the comprehensive nurse-led digital DSMES program with standard digitally delivered education materials.

Outcome Measures

Primary and secondary outcomes will be assessed at baseline (pre-intervention) and at the end of the 12-week intervention.

Primary Outcomes:

1. Self-Management: Assessed using the Type 2 Diabetes Self-Management Scale, which evaluates key aspects of diabetes self-care behaviors.
2. Glycemic Control: Assessed by HbA1c levels obtained from laboratory records.

Secondary

Outcomes:

1. Diabetes Distress: Measured using the Diabetes Distress Scale.
2. Additional Glycemic Parameters: Fasting plasma glucose and postprandial plasma glucose values.
3. Self-Management Behaviors: Assessed using the ADCES7™ Self-Management Behaviors Assessment Form and the Type 2 Diabetes Personal Behavior Goal Tracking Card.
4. Metabolic Parameters: Documented with the Type 2 Diabetes Metabolic Parameter Tracking Form and Metabolic Parameter Goal Tracking Card.
5. Usability and Acceptability of the Digital DSMES Program: Assessed using the Mobile Application Usability Scale (MAUS) among participants in the intervention group.

Ethical Considerations

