The study protocol has been reviewed and approved by the Akdeniz University Faculty of Medicine Clinical Research Ethics Committee (Approval No: TBAEK-1079) and by the relevant institutional authorities at Van Regional Training and Research Hospital. All participants will be informed about the purpose, procedures, potential risks, and benefits of

the study and will provide informed consent before enrollment. Participation is voluntary, and participants may withdraw from the study at any time without any impact on their routine medical care.

Data confidentiality and privacy will be strictly protected. Personal data and clinical information will be stored securely and used only for research purposes in accordance with applicable ethical and legal regulations. The study involves a behavioral and educational intervention considered to be low risk. Adverse events related to the intervention are not expected; however, any unexpected problems will be documented and managed according to institutional policies.

Expected Contribution

It is anticipated that the nurse-led digital DSMES program will significantly improve diabetes self-management behaviors, enhance glycemic control, and reduce diabetes-related distress in young adults with T2DM compared with standard digital education alone. The results of this study may provide evidence to support the integration of nurse-led digital DSMES into routine care for young adults with T2DM, contribute to the development of innovative education models in diabetes nursing, and inform health policy and clinical practice regarding the use of digital health technologies in chronic disease management.

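### Withdrawal criterion 5 takes out randomised participants who start a GLP-1 receptor agonist, with no week-12 assessment provided for, so their questionnaire scores would probably not be collected (minor, nearly cost-free to fix)

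*Protocol*

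**What the plan says.** All references are to the Protocol.

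- **Participants, withdrawal criteria.** The fifth item is "5) initiation of GLP-1 receptor agonist therapy during the study period". The sixth and last item, "any new health condition deemed by the investigator to make continued participation inappropriate", closes the list.
- **Randomization and Blinding.** On timing, this section states: "After baseline assessment, participants will be randomized in a 1:1 ratio to the intervention or active control group". Criterion 5 therefore applies to people who have already been allocated.
- **Outcome Measures, schedule.** "Primary and secondary outcomes will be assessed at baseline (pre-intervention) and at the end of the 12-week intervention". No other assessment time is given, and nothing is said about participants who have been withdrawn.
- **Outcome Measures, the outcomes affected.** Self-management (primary): "Assessed using the Type 2 Diabetes Self-Management Scale, which evaluates key aspects of diabetes self-care behaviors". Diabetes distress (secondary): "Measured using the Diabetes Distress Scale". Both must be obtained from the participant. Glycaemic control (primary) differs: "Assessed by HbA1c levels obtained from laboratory records".
- **Ethical Considerations.** On voluntary withdrawal: "participants may withdraw from the study at any time without any impact on their routine medical care".

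**The concern.** Starting a GLP-1 receptor agonist is a treatment decision taken after randomisation and plausibly related to glycaemia. If it ends participation, the people left at week 12 in each arm have been selected on that decision, and the comparison is no longer quite the one that randomisation set up.

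The criterion also reaches further than its likely purpose. The evident reason for it (an inference, since the protocol gives none) is to keep the drug's effect out of HbA1c. That gives no clear reason to lose the self-management and distress scores. HbA1c may still be found in laboratory records after a withdrawal. A questionnaire that was never completed cannot be recovered by any analysis plan, which is why the question belongs in the protocol.

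**Working it through.** **1. Does withdrawal mean no week-12 assessment?** The protocol does not say, so the wording has to be weighed.

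- *Towards leaving the study:* criterion 6 speaks of continued participation. Criterion 2, in the same list, makes being unable to finish follow-up measurements a ground for withdrawal. Ethical Considerations speaks of withdrawing from the study, although there it describes a participant's voluntary right.
- *Towards stopping only the programme:* criterion 4 ties participation to the share of the intervention received, and the week-12 schedule exempts nobody.

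Leaving the study is the ordinary reading, with some ambiguity.

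**2. How large could the effect be?** The only figure available is the total of 72, which at 1:1 gives 36 per arm. The protocol shown gives no start rate, SD or difference between starters and non-starters, so the other inputs are assumptions:

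- a, b = number of starters in the two arms, taken as 2 v 2, 3 v 1 and 4 v 1 (also 1 v 1 for precision);
- dA, dB = week-12 mean of starters minus non-starters in each arm, in SD units, taken as 0.2 to 0.5 in size;
- starters' scores are wholly missing and the remaining participants are compared without adjustment.

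An arm's full mean is its non-starter mean plus (a/36) × dA. Dropping starters leaves the non-starter mean. The size of the shift in the between-arm difference is therefore

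shift = (a × dA − b × dB) / 36.

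*Same d in both arms:*

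| Starters | d = 0.2 | d = 0.5 |
|---|---|---|
| 2 v 2 | 0 | 0 |
| 3 v 1 | 2 × 0.2/36 = 0.011 | 2 × 0.5/36 = 0.028 |
| 4 v 1 | 3 × 0.2/36 = 0.017 | 3 × 0.5/36 = 0.042 |

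The standard error of the difference with everyone assessed is √(2/36) = 0.236 SD. The largest value in the table is 0.042/0.236 = 0.18 SE.

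*Different d by arm:*

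- 2 v 2, d = 0.5 and 0: (2 × 0.5 − 0)/36 = 0.028 SD.
- 2 v 2, d = 0.5 and −0.5: (2 × 0.5 + 2 × 0.5)/36 = 0.056 SD.
- 4 v 1, d = 0.5 and −0.5: (4 × 0.5 + 1 × 0.5)/36 = 0.069 SD, or 0.069/0.236 = 0.29 SE.

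The shift is zero if nobody starts, if starters do not differ from non-starters, or if a × dA = b × dB. Its sign cannot be told from the protocol.

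**3. Precision.** The standard error is multiplied by √[(1/(36 − a) + 1/(36 − b)) / (2/36)]:

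- 1 v 1: 1.014
- 2 v 2: 1.029
- 3 v 1: 1.029
- 4 v 1: 1.038

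The standard error therefore rises by 1.4% to 3.8%.

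**The case against.** **The loss is not stated.** A reader might infer that the protocol orders starters' scores to be discarded. It does not. Voluntary withdrawal is not the same as withdrawal triggered by a prescription, and criterion 4 allows a reading in which only the programme stops. This stands as a limit on certainty. It does not remove the point, because no provision keeps a starter in assessment and criteria 2 and 6 favour exit.

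**Starts may not differ by arm.** A reader might infer that the intervention prompts prescriptions, since its nurse reviews participants' data and may direct them to a physician. The protocol mentions no prescribing there. Controls can also enter glycaemic data, and both arms come from one clinic. A link with arm is possible and no more.

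**The effect is small.** This stands. The 0.29 SE case needs 4 v 1 starts together with half-SD differences of opposite sign in the two arms, and nothing in the protocol supports that combination. Nor should power losses computed for general dropout of 5% to 20% be attributed to this criterion: that would be about 4 to 14 of 72 people, against 2 to 5 starters in the cases above.

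**The criterion has a rationale.** A new glucose-lowering drug can obscure the effect of education on HbA1c. That is fair for HbA1c, and how post-initiation values are analysed is properly left to the SAP, which is not shown. It gives no clear reason to forgo the two questionnaires.

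**Other withdrawal criteria raise the same question.** The protocol is equally silent on assessment after withdrawal under those. This point is confined to criterion 5 and makes no claim about them.

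**Conclusion.** The point holds as a minor one. Criterion 5 takes randomised participants out because of a later treatment decision, and no week-12 assessment is provided for afterwards. On the ordinary reading, starters' self-management (primary) and distress (secondary) scores would not be collected.

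The likely bias is 0 to 0.04 SD (up to 0.18 SE) if starters differ from non-starters alike in both arms, with a rise of a few per cent at most in the standard error. Its direction is unknown. These sizes rest on assumed start counts and differences. The documents do not support a claim of serious bias, of arm-dependent prescribing, or of a loss that is certain. The case for change is that the loss is avoidable and irreversible, affects a primary outcome, and costs almost nothing to prevent.

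**What to change.** Amend criterion 5 so that starting a GLP-1 receptor agonist:

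- is recorded, with its date, in both arms;
- does not end study participation;
- leaves the participant in the assigned arm for self-management and distress, with the planned week-12 questionnaires completed and HbA1c retrieved from laboratory records.

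Prescribing is unaffected. If the sponsor already intends to assess starters, one sentence saying so is enough.

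**Cost:** a short protocol amendment, one date field, and an assessment that is already scheduled.

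**Downside:** HbA1c in the few starters will reflect the drug. Whether those values enter the main HbA1c comparison is for the SAP to settle.

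### Withdrawing participants after randomisation for not starting, or for taking part in under half of the program, has a clear meaning mainly in the intervention arm and can bias both primary outcomes

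*Protocol*

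**What the plan says.** Four parts of the Protocol bear on this point.

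- **Participants, withdrawal criterion (4).** A participant is withdrawn for "failure to start the program within four weeks after enrollment or participation in less than 50% of the planned intervention". The list of withdrawal criteria is not limited to one arm.
- **Randomization and Blinding.** "After baseline assessment, participants will be randomized in a 1:1 ratio to the intervention or active control group". No account set-up, log-in or run-in is described before allocation. On the digital side, inclusion asks for "access to the internet and ability to use a smartphone, tablet, or computer" and for willingness to take part in digital follow-up. It does not ask for actual use of the platform.
- **Intervention Group and Active Control Group.** The nurse-led arm receives a 12-week program on a dedicated platform. Controls receive the Ministry of Health brochure "in PDF format via the digital platform" and may enter basic glycemic data. No schedule or amount of use is set for them.
- **Outcome Measures.** Both primary outcomes, the self-management scale and HbA1c, are measured at baseline and at the end of the 12 weeks.

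The Protocol does not say whether a withdrawn participant is still measured at 12 weeks or kept in the analysis.

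**The concern.** Criterion (4) selects on behaviour that occurs after allocation. Where the word program names what this trial delivers, it means the nurse-led program, and only that arm has a planned amount of participation of which half could be missed. Someone allocated to it who never opens a module meets the rule plainly. A control who never opens the brochure may or may not meet it, because the text does not say what starting means for a control.

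Not starting, or dropping below half, plausibly marks low motivation, and motivation plausibly bears on both self-management and HbA1c. If these people leave the comparison from one arm and their counterparts stay in the other, the two groups are no longer those that randomisation formed. The direction is predictable: towards the program, which is also the result that the Expected Contribution section anticipates.

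**Working it through.** **Inputs from the Protocol.** The total is fixed by "A total of 72 participants diagnosed with T2DM, aged between 18 and 45 years", and 1:1 allocation gives 72 / 2 = 36 per arm. No error rate, power, effect size, SD or dropout rate accompanies the 72, so it cannot be re-derived. For scale only, with two-sided 5% and a normal approximation, 36 per arm detects (1.96 + 0.84) × sqrt(2/36) = 0.66 SD with 80% power.

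**Inputs that are assumptions.** These are the share *q* of the intervention arm removed under criterion (4), and the gap *g*, in SD, by which those removed would have done worse than those kept. The main illustration uses q = 10% to 20% and g = 0.5. The table widens both. It takes no controls as removed.

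**Shift.** The full-arm mean is (1 − q) × (mean of those kept) + q × (mean of those removed). Using only those kept moves it by q × g:

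- 0.10 × 0.5 = 0.05 SD
- 0.20 × 0.5 = 0.10 SD

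**Standard error.** With 36 against 36 it is sqrt(2/36) = 0.236 SD, so the shifts are 0.05/0.236 = 0.2 and 0.10/0.236 = 0.4 standard errors. After removal it is sqrt(1/36 + 1/(36(1 − q))), as in the table.

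**Two-sided type I error.** With m = q × g / SE, it is 1 − Φ(1.96 − m) + Φ(−1.96 − m).

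| q | removed of 36 | SE | shift (SD) at g = 0.3 / 0.5 / 0.8 | type I error (%) at g = 0.3 / 0.5 / 0.8 |
|---|---|---|---|---|
| 10% | 3.6 | 0.242 | 0.03 / 0.05 / 0.08 | 5.2 / 5.5 / 6.3 |
| 20% | 7.2 | 0.250 | 0.06 / 0.10 / 0.16 | 5.7 / 6.9 / 9.8 |
| 30% | 10.8 | 0.260 | 0.09 / 0.15 / 0.24 | 6.4 / 8.9 / 15.2 |

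The 30% row is there because the second limb, low participation, adds to the non-starters.

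**If controls are removed too.** With a share q_c removed from the control arm and the same gap, the net shift is (q − q_c) × g. For example, (0.20 − 0.10) × 0.5 = 0.05 SD. The bias shrinks as the two shares come together, and the Protocol gives no definition that would bring them together.

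**If everyone is kept.** If non-starters gain nothing, the effect is multiplied by 0.9 to 0.8. For power this equals 72 × 0.9² = 58 to 72 × 0.8² = 46 participants. From an assumed 80% at 0.66 SD, power becomes 71% to 61%. If they are dropped, nominal power is 78% to 75%, but for a comparison carrying the shift above.

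**The case against.** The strongest reply has four parts.

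- **The order of steps is ordinary.** A reader might infer that randomising before first log-in is itself the error. The Protocol does not support that. Baseline assessment followed by randomisation is a legitimate design, and if non-starters were followed and analysed as randomised, the same order would produce no such bias. The harm comes from criterion (4). This part of the reply stands.
- **The rule is not confined to one arm.** A reader might also infer that only the intervention arm can have non-starters. That goes too far. A control may never log in, and other criteria, such as "interruption of internet access or digital communication for more than two weeks", are worded for either arm. What remains is that criterion (4) has a definite meaning in one arm and none in the other.
- **Withdrawn need not mean unanalysed.** An SAP that is not shown may keep these people in the analysis set, so it cannot be said that they are excluded. But an SAP cannot recover 12-week measurements that were never taken, and nothing in the Protocol secures those measurements for withdrawn participants.
- **Dilution is not a defect.** Non-uptake is part of the effect of offering a digital program, and the stated aim is use in routine care. This stands: the lower power when everyone is kept is no argument for removing anyone.

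The size is also modest and rests on assumed inputs: 0.2 to 0.4 standard errors in the main illustration.

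**Conclusion.** The point holds as a criticism of withdrawal criterion (4), both limbs, and not of the timing of randomisation. As worded, it takes low-engagement participants out of the study after allocation, mainly and apparently only from the intervention arm. The consequence is conditional: if those withdrawn leave follow-up or the analysis, both primary comparisons are biased towards the program.

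At the assumed 10% to 20% non-start and 0.5 SD gap, type I error rises from 5% to between 5.5% and 6.9%. Larger gaps, or adding the low-participation limb, make it worse. These figures further assume no adjustment for baseline and no matching removal of controls. The bias is small beside the sampling error, but it is one-directional and can be avoided at little cost, so the change should be made before recruitment.

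**What to change.** 1. Remove both limbs of criterion (4) as grounds for withdrawal from the study. Record failure to start and participation below half as non-adherence to the program only.
2. State that these participants are measured at 12 weeks on both primary outcomes and analysed in the arm to which they were randomised.
3. As a supplement, have every participant set up the account and log in once to a neutral page before randomisation, and randomise only those who do. Both arms receive their material through the platform, so this is feasible.

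Steps 1 and 2 cost a change of wording and the effort of obtaining 12-week measurements from people who did not engage. Against a starters-only analysis they also give up some nominal power, as shown above, in return for an unbiased estimate of the effect of offering the program.

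Step 3 costs one landing page and a few more people to consent, and it limits the sample to those who activate. It cannot replace step 1. One log-in does not show that a person will start a 12-week program, and someone who logs in and then opens no module would still fall under the low-participation limb if that limb stayed.

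### Does a start delay of up to four weeks, with HbA1c read from laboratory records, distort the timing of the primary HbA1c comparison?

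*Protocol*

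**What the plan says.** The Outcome Measures section names HbA1c as the second primary outcome: "Assessed by HbA1c levels obtained from laboratory records". The sentence introducing the outcomes fixes when they are measured: "Primary and secondary outcomes will be assessed at baseline (pre-intervention) and at the end of the 12-week intervention". The Study Design section gives the length of follow-up under treatment: "The intervention period for each participant is 12 weeks".

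Three other statements bear on timing:

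- **Order of events** (Randomization and Blinding): "After baseline assessment, participants will be randomized in a 1:1 ratio to the intervention or active control group using stratified block randomization".
- **Tolerated delay** (Participants, withdrawal criterion 4): a participant is withdrawn for "failure to start the program within four weeks after enrollment or participation in less than 50% of the planned intervention". A shorter delay is therefore allowed.
- **Control condition** (Active Control Group): "Participants in the active control group will be provided with access to the standard Type 2 Diabetes Education Brochure", delivered through the digital platform, with the option to enter basic glycemic data. No separate start or end is described for this arm.

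The Protocol gives no acceptance window around the laboratory value and no rule for choosing among several values.

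**The concern.** HbA1c reflects glycemia over the preceding weeks, so the date of the sample matters. Two features look worrying on a first reading.

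First, the endpoint is tied to the end of the intervention and not to randomization, and the program may begin up to four weeks after enrollment. A participant in the nurse-led arm might be measured about 16 weeks after enrollment. A control participant, who only needs access to a PDF, might be measured at about 12. Any background change under routine care over the extra weeks would then be mixed with the treatment effect.

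Second, a value taken from laboratory records might be whichever routine result lies nearest. An endpoint value drawn early would still contain glycemia from before the program and would understate the effect. With 72 participants there is little room for such loss on a primary outcome.

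**Working it through.** **Inputs from the Protocol.** Intervention length 12 weeks; tolerated delay L from enrollment to program start of 0 to 4 weeks; assessment at the end of the intervention; 72 participants at 1:1, so 72 / 2 = 36 per arm. The Protocol states no significance level, power, effect size, standard deviation or dropout rate, so there is no sample-size figure to reproduce.

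**Step 1: what the delay moves.**

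| Clock | Delay L | Weeks from enrollment to assessment | Planned weeks of exposure |
|---|---|---|---|
| Program start (as written) | 0 | 12 + 0 = 12 | 12 |
| Program start (as written) | 2 | 12 + 2 = 14 | 12 |
| Program start (as written) | 4 | 12 + 4 = 16 | 12 |
| Enrollment (not as written) | 0 | 12 | 12 − 0 = 12 |
| Enrollment (not as written) | 2 | 12 | 12 − 2 = 10 |
| Enrollment (not as written) | 4 | 12 | 12 − 4 = 8 |

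Under either clock the delay moves one quantity and leaves the other fixed. Under the Protocol's wording the one that moves is time since enrollment, by at most 4 / 12 = 33% of the nominal period.

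**Step 2: where a large power loss would come from.** Assume that glucose changes in one step at program start and that HbA1c weighting falls linearly to zero over T weeks. The visible share of the full change after t weeks is f(t) = 1 − (1 − t/T)².

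- T = 17: f(8) = 0.720, f(12) = 0.913, ratio 0.788.
- T = 15: f(8) = 0.782, f(12) = 0.960, ratio 0.815.

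Assume also that the trial has 80% power at two-sided 0.05 with 36 per arm, which corresponds to about 0.67 SD. Taking a ratio of about 0.80, the effect shrinks to 0.67 × 0.80 = 0.536 SD and power falls to about 61%.

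The arithmetic is sound, but it compares 8 with 12 weeks of exposure. By Step 1 the start delay never yields 8 weeks under the Protocol's clock. The figure would need every endpoint sample to be drawn four weeks early, and no statement in the Protocol provides for that.

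**Step 3: what the delay could do.** If the arms had different mean delays, the bias would be roughly the difference in mean delay (at most 4 weeks) times the weekly background drift in HbA1c. The Protocol supplies neither quantity. Four weeks is the point at which a participant is withdrawn, not an expected delay.

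**Step 4: what the alternative clock would do.** Assessing 12 weeks after randomization whatever the start date gives a participant who starts four weeks late 12 − 4 = 8 weeks of exposure, if enrollment and randomization coincide. If the effect were proportional to exposure (an assumption), with 80% power at 0.66 SD by the normal approximation, mean delays of 1, 2 and 4 weeks in the intervention arm would reduce power to about 73%, 65% and 46%. That clock can therefore produce the loss that prompted the concern, unless everyone starts promptly.

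**The case for a change.** The best case for a change has three parts.

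**A treatment-dependent clock.** An endpoint tied to program end, not to randomization, can give the arms different follow-up. The word program is used mainly for the nurse-led package, and the brochure arm has no described start. This stands as a possibility only. The four-week criterion sits in a list that applies to all participants, both arms receive their material through the platform, and the 12-week period is stated for every participant. One clock for both arms is a natural reading.

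**Record-based values.** An analysis plan can define a window, but it cannot supply a blood sample that nobody scheduled. An old baseline value could also place a participant in the wrong HbA1c stratum. This is the stronger half. However, the reference to laboratory records names the source of the data, and the sentence introducing the outcomes fixes the time. Reading it as permission to use any routine result goes beyond the text. A baseline value from before randomization is what the design intends; only a stale one would matter.

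**Differential testing.** The nurse-supported arm might be tested more often. The reminders described are for data entry, and referral to clinicians is made only as needed. The phrase "HbA1c (when available" concerns what participants record in a self-monitoring tool, not the primary outcome. None of this shows that the timing of laboratory tests differs by arm.

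What stands is limited: no explicit start of the clock for control participants, and no window around the two HbA1c values.

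**Conclusion.** No change to the plan is called for. As written, the tolerated delay shifts the endpoint from 12 to as much as 16 weeks after enrollment and leaves planned exposure at 12 weeks. The power figure of about 61% does not follow from the delay. It depends on universal early sampling, an assumed HbA1c weighting curve and an assumed 80% power design. A difference in timing between arms is conceivable, but the text does not state it and the documents offer no figures from which to size it.

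The missing details are an explicit 12-week clock for the control arm and an acceptance window for the laboratory values. Study staff and analysts would ordinarily settle these by running the same 12 weeks in both arms and using the result closest to each planned assessment. A window rule is also commonly placed in a statistical analysis plan, which is not at hand. The choice between counting from program start and counting from randomization is a fair trade-off: the first protects exposure, the second protects calendar time. This conclusion rests on reading the outcome-timing sentence as governing the laboratory HbA1c and on both arms following the same 12-week period.
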